6.1.1 Infusion interruption/dose modification due to CNS events

Please see Appendix E for the grading of CNS-related AEs. In case of CNS-related AEs, dexamethasone should be administered at a dose of at least 24 mg/day. The dexamethasone dose

will then be reduced step-wise over approximately 4 days. The following investigations should be performed:

If the CNS-related adverse event is CTCAE grade 3 or higher, blinatumomab will be stopped immediately and a physical exam, vital signs and safety laboratory tests will be performed. Additional measures can be taken at the discretion of the investigator, depending on the nature of the adverse event. The following diagnostic investigations are recommended:

1. A non-contrast CT scan of the head to exclude CNS hemorrhage.
2. Assessment of cerebrospinal fluid should be performed for cytology, cell count, B- and T-cell measurement (by flow cytometry), and viral studies (HSV 1/2, HSV6, JC virus and adenovirus).
3. Additional investigations of the CSF should be performed as clinically appropriate.
4. A contrast-enhanced magnetic resonance imaging (MRI) of the head should be performed for subjects who had to interrupt treatment because of a CNS event grade 3, before treatment is resumed.

Please note that there may be circumstances in which some of the above investigations will not be able to be performed (for example, CSF assessment may not be possible in patients with low platelet counts or abnormal coagulation parameters, for safety reasons, and MRI may not be possible if patients are unable to lie still for the duration required to perform this examination). Therefore, not performing these tests will not be considered protocol deviations.

For subjects who experience a CTCAE grade 3 CNS adverse event or serious adverse event leading to treatment interruption, if the event has decreased to at least CTCAE grade 1 within 1 week, treatment may be restarted within 2 weeks, but not earlier than 72 hours (3 days) after the infusion was stopped. When recommenced, treatment will begin at the next lowest dose.

However, a grade 3 CNS event leading to treatment interruption at the dose of 9 µg/day or a CNS event needing more than 1 week to resolve to grade less than or equal to 1 will result in permanent treatment discontinuation.

In case of CNS-related events CTCAE grade 4, or in case of occurrence of more than one generalized seizure (considered grade 3 CNS toxicity), the infusion of blinatumomab will be stopped immediately and treatment will be permanently discontinued.

For patients in whom the criteria for recommencement of blinatumomab, as described above, are met, blinatumomab can be recommenced, following dexamethasone premedication as described in Table 1, at the next lowest dose. Blinatumomab will be escalated to the next highest dose after 7 days, if the toxicity does not recur. The subject should remain hospitalized until at least 2 days after re-escalation to the dose at which the toxicity first occurred.

If the CNS event was a generalized seizure (CTCAE grade 2 or above), appropriate prophylactic anticonvulsant treatment will be administered prior to recommencing therapy.

6.1.2 Dose interruption and modification for cytokine release syndrome (CRS) and/or DIC/coagulopathy

For CTCAE grade 2 CRS which requires inotropes, grade 3 CRS and CTCAE grade 3 DIC/coagulopathy, blinatumomab can then be restarted at the next lowest dose (see table 2), once the event has returned to grade ≤ 1 severity. If the event occurred at a dose of 9 mcg/day and no neurological toxicity of greater than or equal to grade 3 occurred, treatment with blinatumomab will be interrupted until the event resolves to less than or equal to grade 1 and then resumed at 9 mcg/d, after dexamethasone pre-medication as described in Table 1. However, if the AE lasts for ≥ 2 weeks, then blinatumomab will be permanently discontinued.

In CRS of \geq grade 2, dexamethasone should be administered orally or IV at an initial dose of at least 3 x 8 mg/day. The dose can then be reduced step-wise over approximately 4 days according to clinical response.

6.1.3 Dose interruption and modification for all other events

For all other CTCAE grade 3 events and clinically significant laboratory value changes, investigator assessment should be used to determine causation. If considered to be at least possibly related to blinatumomab, the blinatumomab must be interrupted. Blinatumomab can be recommenced after resolution of the AE to grade 1 or less, after dexamethasone pre-medication as described in Table 1.

6.1.4 Resumption of dosing and dose escalation after dose interruption

Patients who have had their dose interrupted, who meet the safety criteria outlined above, will have an option to resume dosing, once the event has resolved to grade ≤ 1 , after the time periods outlined for the specific AEs above and in table 2. Please note that, in the event of grade 3 neurological toxicity, the blinatumomab must not be resumed for at least 72 hours after interruption, in addition to waiting for the event to resolve to grade ≤ 1 . After all other reasons for interruption, blinatumomab may be resumed when the toxicity has resolved to grade ≤ 1 .

Pre-medication will be given with 20mg of PO/IV dexamethasone 12-24 hours prior and 20mg dexamethasone 1 hour prior to recommencement of the infusion, as per table 1.

Dosing should be resumed at the next lowest dose level (i.e. 9 $\mu\text{g}/\text{day}$ if the AE occurred at 28 $\mu\text{g}/\text{day}$ or 28 $\mu\text{g}/\text{day}$ if the AE occurred at 112 $\mu\text{g}/\text{day}$). After 7 days of dosing, provided the patient is clinically stable, dose escalation may resume per protocol, with appropriate dexamethasone pre-medication (as outlined in table 1). Alternatively, treatment may be continued at the reduced dose after discussion with the principal investigator, if it is felt that the risks of further dose escalation outweigh the benefits. Re-start of the infusion and all subsequent dose escalations should be performed in the hospital.

The patient should be observed in hospital for the remainder of the dose re-escalation period and for 3 days after reaching the highest dose that will be administered in that cycle.

The total duration of blinatumomab in cycle 1 and 2 should total 28 days. If dose interruptions occur, the missed days should be added to the end of the cycle. The total number of days of blinatumomab administration will not exceed 28 days, even if dose reductions occurred. An infusion interruption of more than 2 weeks due to an adverse event related to blinatumomab will lead to permanent discontinuation of treatment. In case of logistical difficulties, restart of treatment can be postponed for up to 7 additional days without resulting in permanent treatment discontinuation. Treatment may be also interrupted or permanently discontinued at the discretion of the investigator if any clinical/laboratory adverse event is considered to be medically relevant.

If there is recurrence of grade ≥ 3 toxicity, determined as at least possibly related to blinatumomab, after reinstitution of blinatumomab, blinatumomab will be permanently discontinued.

For the sake of clarity, if blinatumomab is interrupted and subsequently recommenced, the days when blinatumomab was not given will not be counted as treatment days. e.g. If treatment was interrupted on day 7 for 3 days and then recommenced, the day that blinatumomab was recommenced will be numbered as day 8, not day 11.

Nivolumab (in the absence of nivolumab-related adverse events requiring treatment interruption) will always be given on day 1 and day 15 of blinatumomab treatment. For this reason, if there are delays in blinatumomab administration due to adverse events, there will be an identical delay in administration of the next nivolumab dose. This is important both for reasons of clarity and also because nivolumab could potentiate blinatumomab-related adverse events.

6.2 Recommendations for management of nivolumab-associated toxicity.

Please see appendix K.

6.3 - management of ibrutinib-associated toxicity and dose modifications

Section 6.3 outlines recommendations for management of ibrutinib-associated toxicity. However, dose adjustments outside these guidelines can be made by the investigator if considered to be in the patient's best interests.

6.3.1 Recommended dose modifications:

Recommended dose modifications of ibrutinib are described below:

Toxicity Occurrence	Dose modification Starting Dose = 420 mg daily
First	Restart at 420 mg daily
Second	Restart at 280 mg daily
Third	Restart at 140 mg daily
Fourth	Discontinue ibrutinib

Interrupt ibrutinib for any Grade 3 or greater neutropenia with infection or fever, or Grade 4 hematological toxicities. Once the toxicity has resolved to Grade ≤ 1 or baseline, reinitiate ibrutinib as

per the table above.

6.3.3 Non-hematologic toxicity:

Interrupt treatment for any grade 3 or greater non-hematological toxicity. Once the toxicity has resolved to grade ≤ 1 or baseline, restart the study drugs as per the guidelines for the hematologic toxicity as above.

If the dose of ibrutinib is reduced, at the investigator's discretion, the dose of ibrutinib may be re-escalated after 2 cycles of a dose reduction if the toxicity that led to the reduction has resolved to Grade ≤ 1 or baseline. Dose changes will be recorded in the medical record.

6.3.4 Leukocytosis/Leukostasis:

A high number of circulating malignant cells ($>400000/\text{mcL}$) may confer increased risk of leukostasis; these subjects should be closely monitored. Administer supportive care such as hydration and/or leukapheresis as indicated. Ibrutinib may be temporarily held, and investigator should be contacted.

6.3.5 Dose Modification for Hepatic Impaired Subjects

Ibrutinib is metabolized in the liver and therefore subjects with clinically significant hepatic impairment at the time of screening (Child- Pugh class B or C) are excluded from study participation. For patients with mild liver impairment (Child-Pugh class A), recommended dose is 140mg per day. See Appendix L for Child-Pugh grading system.

6.3.6 Dose Modification of Ibrutinib in patients receiving CYP3A4 enzyme inhibitors and inducers:

Co-administration with strong or moderate CYP3A inhibitors should be avoided, where possible and alternative agents with less CYP3A inhibition considered.

Concomitant use of strong CYP3A inhibitors which would be taken chronically (e.g., ritonavir, indinavir, nelfinavir, saquinavir, boceprevir, telaprevir, nefazodone) is not recommended. For short-term use (treatment for 7 days or less) of strong CYP3A inhibitors (e.g., antifungals and antibiotics) consider interrupting ibrutinib therapy until the CYP3A inhibitor is no longer needed.

Reduce ibrutinib dose to 140 mg if a moderate CYP3A inhibitor must be used (e.g., fluconazole, darunavir, erythromycin, diltiazem, atazanavir, aprepitant, amprenavir, fosamprenavir, crizotinib, imatinib, verapamil, and ciprofloxacin).

Patients taking concomitant strong or moderate CYP3A inhibitors should be monitored more closely for signs of ibrutinib toxicity.

Use of strong CYP3A4 enzyme inducers (eg. rifampicin) should be avoided.

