3.2 Exclusion Criteria

1. Other active malignancy receiving systemic therapy.
2. History or presence of clinically relevant disorder affecting the CNS such as epilepsy, childhood or adult seizure, paresis, aphasia, stroke, severe brain injuries, dementia, Parkinson's disease, cerebellar disease, organic brain syndrome, or psychosis, with the exception of a history of CNS lymphoma that is controlled with intrathecal therapy.
3. Known active DLBCL in the CNS (confirmed by CSF analysis).
4. Current autoimmune disease requiring >/= 20mg/day of prednisone or systemic immunosuppressive therapy (eg. With cyclosporine or azathioprine).
5. Allogeneic HSCT within 24 weeks before the start of protocol-specified therapy.

6. Active Graft-versus-Host Disease (GvHD), grade 2-4 according to the Glucksberg criteria, active chronic GvHD requiring systemic treatment or requirement for systemic GvHD prophylaxis with cyclosporine or tacrolimus.
7. Cancer chemotherapy within 2 weeks before start of protocol-specified therapy, with the exception of intrathecal chemotherapy, dexamethasone, and oral small molecule inhibitors such as BTK-inhibitor, PI3K-inhibitor, or Bcl-2-inhibitor, which are allowed until the start of protocol-specified therapy). In addition, any subject whose organ toxicity (excluding hematologic) from prior treatment has not resolved to no more than CTCAE grade 1
8. Radiotherapy within 2 weeks before the start of protocol-specified therapy
9. Abnormal screening laboratory values as defined below:
 - ALT (SGOT) and/or ALT (SGPT) and/or ALP $\geq 5 \times$ upper limit of normal (ULN)
 - Total bilirubin $\geq 1.5 \times$ ULN, unless due to Gilbert's disease
 - Creatinine $\geq 2.0 \times$ ULN or creatinine clearance $<50 \text{ mL/min}$ (calculated)
10. Known infection with human immunodeficiency virus (HIV) or chronic infection with hepatitis B virus (HBsAg positive) or hepatitis C virus (anti-HCV positive)
11. Patient is pregnant or breast feeding
12. Woman of childbearing potential and is not willing to use 2 highly effective methods of contraception while receiving protocol-specified therapy and for an additional **5 months** after the last dose of protocol-specified therapy
13. Male who has a female partner of childbearing potential or a pregnant partner, and is not willing to use a condom during sexual activity while receiving protocol-specified therapy and for **7 months** after the last dose of protocol-specified therapy

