4.0 TREATMENT PLAN

This is a single arm, open label, phase II study of ibrutinib, nivolumab and blinatumomab in patients with RT.

[figure not shown]

Figure 4. Schematic of treatment plan

Patients will receive treatment as follows:

1. 2 cycles of 3 drug combination (ibrutinib, nivolumab and blinatumomab). These cycles will be 8 weeks each.
2. 9 cycles of 2 drug combination (ibrutinib and nivolumab). These cycles will be 4 weeks each.
3. Maintenance treatment with ibrutinib monotherapy until disease progression following completion of nivolumab.

4.1 Ibrutinib therapy.

Ibrutinib treatment will commence on cycle 1, day 1 at 420mg/d. Dose reductions to 280mg/d or 140mg/d are allowed per treating physician discretion, but the reason must be documented in the medical record. Ibrutinib will be given continuously until disease progression or toxicity.

4.2 Nivolumab therapy.

Patients will receive nivolumab for up to a total of 52 weeks. Dosing will be 240mg IV every 2 weeks, commencing on day 1 until 2nd response assessment, then 480mg IV every 4 weeks.

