examination must also be performed — all subsequent physical examinations, can be focused to the individual needs of the individual patient.

⁷A neurological examination must be performed during the screening period. Neurological examination at the screening assessment should include examination of the peripheral nervous system, cranial nerves and cognitive function. The latter must be determined using The M.D. Anderson simplified 10 point neurologic examination. Subsequent to the screening exam, the neurological assessment can be tailored, according to the patient's symptoms. Whenever there is a change in neurological status suggestive of blinatumomab-related neurotoxicity, the M.D. Anderson 10 point neurological examination score will be documented, to assist toxicity grading (see Appendix E and G).

⁸Concomitant medications. These will be captured in the medical record.

⁹Complete blood count with differential.

¹⁰Biochemistry. At screening, at a minimum this should include the following: sodium, potassium, chloride, bicarbonate (or total carbon dioxide [CO₂]), blood urea nitrogen (BUN, or urea), random glucose, albumin, creatinine, total bilirubin (direct and indirect), ALT +/- AST, alkaline phosphatase, phosphorous, calcium, uric acid and LDH. At subsequent timepoints, this should include, at a minimum, creatinine, potassium and ALT. On the day of and for two days after dose initiation or dose escalation, uric acid, calcium and phosphorous should be measured at least daily.

¹¹Thyroid function (at least TSH and T4) is required at baseline and approximately every 4 weeks during the study to monitor for nivolumab-induced hypothyroidism, until the completion of nivolumab therapy.

¹²Bone marrow examination Bone marrow aspiration and trephine biopsy will be performed pre-treatment for cytological and histological assessment during the screening period. The following additional studies will be performed on the pre-treatment bone marrow and on bone marrow evaluation performed at disease progression: CLL prognostic marker evaluation on bone marrow (or blood if bone marrow not available): FISH, using probes for ATM (11q22.3), D12Z3 (12cen), D13S319 (13q14.3), LAMP1 (13q34), p53 (17p13.1); stimulated metaphase cytogenetics; next

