Appendix L. Child-Pugh Grading System for Cirrhosis.

Child-Turcotte-Pugh Classification for Severity of Cirrhosis			
Clinical and Lab Criteria	Points*		
	1	2	3
Encephalopathy	None	Grade 1 or 2	Grade 3 or 4
Ascites	None	Mild to moderate (diuretic responsive)	Severe (diuretic refractory)
Bilirubin (mg/dL)	< 2	2-3	>3
Albumin (g/dL)	> 3.5	2.8-3.5	<2.8
Prothrombin time Seconds prolonged or International normalized ratio	<4 <1.7	4-6 1.7-2.3	>6 >2.3

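### Section 6.3.5 says Child-Pugh class B or C patients are excluded, but the Section 3.2 list has no such criterion and the required screening tests omit the PT/INR needed to assign the class

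*Combined protocol and SAP*

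**What the plan says.** Section 6.3.5 states as a fact about the trial that "subjects with clinically significant hepatic impairment at the time of screening (Child- Pugh class B or C) are excluded from study participation". It continues: "For patients with mild liver impairment (Child-Pugh class A), recommended dose is 140mg per day. See Appendix L for Child-Pugh grading system". The Child-Pugh class is therefore meant to bear on eligibility and on ibrutinib dose.

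Eligibility itself is set in Section 3.2. Item 9 there ("Abnormal screening laboratory values as defined below") gives limits for transaminases and ALP (5 × ULN), for bilirubin ("Total bilirubin $\geq 1.5 \times$ ULN, unless due to Gilbert's disease") and for creatinine. Item 10 excludes chronic hepatitis B or C infection. Item 16 lets the Principal Investigator exclude a patient for another clinically significant disorder. No item mentions Child-Pugh class or hepatic impairment.

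Appendix L scores encephalopathy, ascites, bilirubin, albumin and "Prothrombin time Seconds prolonged or International normalized ratio". The screening chemistry is set out in footnote 10 to Table 4 (Section 9.0). It is described as a minimum and includes albumin as well as "total bilirubin (direct and indirect), ALT +/- AST, alkaline phosphatase, phosphorous, calcium, uric acid and LDH". Hematology is a complete blood count with differential. Neither Table 3 nor Table 4 schedules PT, INR or any other coagulation test.

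**The concern.** An exclusion that appears only in a dose-modification section may be missed by whoever confirms eligibility against Section 3.2. A patient whom one part of the protocol describes as excluded could then satisfy every listed criterion and start ibrutinib. The protocol gives its own reason for caring: Section 5.3.4 reports single-dose ibrutinib AUC increases of 2.7-, 8.2- and 9.8-fold in Child-Pugh classes A, B and C compared with normal liver function.

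Even a site that knows of the Section 6.3.5 rule is not required to collect everything needed to apply it.

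**Working it through.** This is a check of consistency between sections. The plan gives no figure to reproduce, and the only arithmetic is the Appendix L score.

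**1. Is the rule anywhere in the eligibility criteria?** The exclusion list runs from 1 to 17 without a gap, and the inclusion list has 4 items. None names Child-Pugh class or hepatic impairment. Component by component:

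| Appendix L component | Limit in Section 3.2 | Required at screening |
|---|---|---|
| Encephalopathy | No hepatic criterion (item 2 covers certain CNS disorders) | Neurological examination |
| Ascites | None | History and physical examination; no specific item |
| Bilirubin | Item 9, 1.5 × ULN, Gilbert's excepted | Yes |
| Albumin | None | Yes |
| PT or INR | None | No |

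The enzymes limited in item 9 are not Child-Pugh components.

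**2. Does the bilirubin limit imply the rule?** The documents give no bilirubin ULN, so a range is assumed.

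- ULN 1.0 mg/dL: limit 1.5 × 1.0 = 1.5 mg/dL
- ULN 1.3 mg/dL: limit 1.5 × 1.3 = 1.95 mg/dL

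Appendix L gives 1 point below 2 mg/dL. Over this range, everyone who passes the limit scores 1 for bilirubin, apart from patients under the Gilbert's exception. At a ULN of 1.4 the limit would be 2.1 mg/dL and a passing patient could score 2, which makes class B easier to reach.

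Example: bilirubin under 1.5 × ULN (1) + albumin below 2.8 g/dL (3) + mild ascites (2) + no encephalopathy (1) + INR below 1.7 (1) = 8. Class B is 7 to 9. No numeric limit in Section 3.2 is met, provided transaminases, ALP and creatinine are also within limits.

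More generally, fix bilirubin and encephalopathy at 1 point each. Ascites, albumin and PT/INR then have 3 × 3 × 3 = 27 point combinations, with totals from 5 to 11. Of these, 4 are class A, 19 class B and 4 class C. These are combinations of scores and say nothing about how often such patients occur.

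**3. Can the class be assigned without PT/INR?** The other four components total 4 to 12, and PT/INR adds 1 to 3.

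| Subtotal without PT/INR | Possible totals | Possible class |
|---|---|---|
| 4 | 5–7 | A or B |
| 5 | 6–8 | A or B |
| 6 | 7–9 | B |
| 7 | 8–10 | B or C |
| 8 | 9–11 | B or C |
| 9 or more | 10 or more | C |

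The boundary that decides exclusion, A against B, is open at subtotals 4 and 5. For instance, albumin of 2.8 to 3.5 g/dL (2) with the other three components at 1 gives a subtotal of 5: class A if PT/INR scores 1 (total 6), class B if it scores 2 (total 7). The example in step 2 has a subtotal of 7, so it is at least class B whatever the INR. The two gaps are therefore separate: the missing criterion matters even when the class is clear, and the missing test matters near the boundary.

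**The case against.** The best defence is that Section 6.3.5 is itself protocol text, so the exclusion exists wherever it is printed. Item 16 lets the investigator exclude a patient with significant liver disease, item 10 removes chronic viral hepatitis, and the chemistry list is only a minimum, so a site may add PT/INR. All of this is true and it lowers the risk. It does not close the gap: item 16 is a matter of judgement, a minimum list permits a test without requiring it, and a categorical exclusion should not depend on either.

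It is also fair that Section 6.3.5 concerns patients with hepatic impairment and that Appendix L is a grading system for cirrhosis. PT/INR is thus needed where impairment is suspected, and the documents do not ask for every patient to be scored. For the same reason, a reader might infer too much from the lowest possible score of 5 being class A, namely that every enrolled patient falls under the class A dose statement. The text attaches the class to patients who have mild impairment, so that inference is weak.

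A reader might also see a flat dose contradiction between "Ibrutinib treatment will commence on cycle 1, day 1 at 420mg/d" in Section 4.1 and "For patients with mild liver impairment (Child-Pugh class A), recommended dose is 140mg per day" in Section 6.3.5. Section 4.1 goes on to allow 280 or 140 mg/d at the treating physician's discretion, and Section 6.3 permits adjustments outside its guidelines. What remains is mostly a missing cross-reference between a general dose and a special-population statement.

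Finally, a reader might connect the gap to the toxicity stopping rule. The toxicity monitored in Section 14.0 is specified neurotoxicity and CRS, plus grade 3–5 immune-related toxicity at least possibly related to nivolumab. It is not aimed at ibrutinib toxicity, so the documents do not support that link.

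**Conclusion.** The inconsistency stands. Section 6.3.5 asserts an exclusion that Section 3.2 does not contain and that its laboratory limits do not imply. The required screening tests also lack one of the five inputs to the score on which the exclusion rests. A patient scoring 8, class B, can meet no listed numeric limit. This assumes a bilirubin ULN of 1.0 to 1.3 mg/dL, with enzymes and creatinine within limits.

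The consequence is for consistent eligibility and for ibrutinib safety. How many patients it would touch cannot be judged from the documents. The 8.2- and 9.8-fold AUC figures are single-dose results; they show why the class matters but do not measure harm in this trial. Sample size, stopping boundaries and primary analysis do not change. The correction should be made because it is specific and cheap, but it is not a flaw in the statistical design.

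**What to change.** The sponsor should reconcile Section 6.3.5 and Appendix L with Section 3.2 and Tables 3 and 4, so that hepatic eligibility is stated once and consistently.

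- If the Child-Pugh rule is retained, list it in Section 3.2, require PT/INR at screening in Tables 3 and 4 and footnote 10, and state which patients are to be scored.
- If it is not retained, amend the statement in Section 6.3.5 to agree with Section 3.2.
- In either case, cross-reference the ibrutinib starting-dose statements in Sections 4.1, 5.3, 6.3.1 and 6.3.5 so that they read together.

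Which eligibility rule and which dose are right is for the sponsor to decide, and this point takes no view on either. The cost is protocol wording and, if the rule is kept, one routine laboratory value at screening.
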